## **13 STUDY DRUG MATERIALS AND MANAGEMENT**

### **13.1 Study Drug**

Vicinium™ (oportuzumab monatox) is a clear, colorless solution for intravesical administration. It is provided as a frozen product in a glass vial, and then thawed at room temperature prior to preparation for administration. Cloudiness, a change in color and/or the presence of particulate matter may indicate the product has deteriorated. If this occurs, Eleven Biotherapeutics Inc. should be contacted immediately and the product must not be used.

### **13.2 Study Drug Packaging and Labeling**

Vicinium is packaged in a 10 mL glass borosilicate vial containing 7 mL of study drug at a concentration of 5 mg/mL. Each vial is sealed with a grey butyl stopper and covered with an aluminum cap center tear-off seal.

Vicinium will be mixed with phosphate buffered saline prior to intravesical administration. Refer to the Vicinium Dose Preparation and Administration Manual for details

### **13.3 Study Drug Accountability**

The Investigator agrees that the study drug will be administered only to subjects who have provided written informed consent, have met all entry criteria, and are enrolled in the study. The Investigator must not loan or dispense clinical study material to another Investigator or site.

Drug accountability records will be maintained by the Investigator or authorized site staff for all clinical trial supplies (includes Vicinium and phosphate buffered saline). Eleven Biotherapeutics Inc. or designee will provide the Investigator with drug accountability logs to document receipt and dispensing. Any discrepancy and/or deficiency must be recorded, reported to Eleven Biotherapeutics Inc. or designee, and a plan for resolution documented. If at any point in the conduct of the study a vial is deemed unacceptable for use, the site will document the damage on the drug accountability log and immediately notify Eleven Biotherapeutics Inc. or designee. Eleven Biotherapeutics Inc. or designee will monitor the completeness and accuracy of all accountability records throughout the study and verify product accountability against site documentation. Any expired Vicinium, or Vicinium vial deemed unacceptable for use or any Vicinium supply remaining at the end of the study should be destroyed at each clinical site in accordance with the site's drug destruction policy.

## **14 ASSESSMENT OF EFFICACY**

Standard white-light cystoscopy, urine cytology, and cystoscopic bladder biopsies (directed) will be performed at Screening as described in **Section 10.1**. Fluorescence cystoscopy (e.g., blue light cystoscopy) is acceptable but not required. If a subject undergoes fluorescence cystoscopy for biopsy or TURBT during the screening period, this modality should be used for all on-study biopsies

or TURBTs. However, white-light cystoscopy is appropriate for routine follow-up assessments if a biopsy is not required.

Subjects' disease status will be evaluated based on cystoscopy (and biopsies if indicated) and urine cytology at the end the Induction Phase (week 13) and every 13 weeks during the Maintenance Phase (i.e., Week 26, Week 39, Week 52, Week 65, Week 78, Week 91, Week 104) regardless of dosing interruptions or delays. For subjects who discontinue treatment for reasons other than disease progression ([Section 14.2](#)), cystectomy or death, the every 13-week disease evaluation should continue for the determination of secondary endpoints e.g., event-free survival, progression-free survival. Every effort should be made to stay on this evaluation schedule, however, a window of one week before and up to 2 weeks after these time points is permitted (e.g., the Week 26 cystoscopy and urine for cytology may be performed from week 25 to week 28, but as close to Week 26 as possible). The complete evaluation to determine disease status may require a repeat cytology and repeat cystoscopy with biopsies (See [Table 7](#)) and should be completed as soon as possible following the every 13-week timepoint. On cystoscopy, any areas suspicious for disease must be biopsied. In situations where there are no suspicious lesions on cystoscopy but a positive or suspicious result on urine cytology, random bladder biopsies will be obtained from the locations of disease identified at Screening (i.e., by screening biopsies and the screening bladder mapping) and from other areas of the bladder so that all the following areas of the bladder have been biopsied: the dome, the posterior wall, the left and right lateral walls, the trigone and the bladder neck, and in males, the prostatic urethra. A second urine cytology will also be required at the time of evaluation if the result of the first urine cytology is suspicious for urothelial carcinoma. The use of other diagnostic evaluations (e.g. urine FISH) or the performance of additional urine cytology, cystoscopies, and/or biopsies not mandated by the protocol may be performed when clinically indicated per the investigator's clinical judgment or standard of care. Results of urine FISH will not be considered in the response evaluation but may be used by the investigator to guide additional (non-protocol mandated) evaluations.

All cytology and biopsy samples (protocol-mandated or additional per investigator discretion) must be centrally reviewed and graded by an independent pathologist with specific expertise in NMIBC. Instructions for shipping and handling of tissue, cytology and EpCAM samples will be provided in the separate Laboratory Manual for Pharmacokinetics, Anti-Drug/Anti-Toxin Antibodies, Cytology and Tumor Tissue Assessments.

**Table 6: Required Tests for Disease Status: Every 13-Week Evaluation**

Cystoscopy	1 st Urine Cytology	Bladder Biopsies	2 nd Urine Cytology
Required	Required	

Directed biopsy of all suspicious-appearing lesions/areas on cystoscopy.

If cystoscopy reveals no suspicious lesions but 1st urine cytology is suspicious or positive for urothelial carcinoma: Biopsy the locations of disease identified at Screening (i.e., by screening biopsies and the screening bladder mapping) and from other areas of the bladder so that all the following areas of the bladder have been biopsied: the dome, the posterior wall, the left and right lateral walls, the trigone and the bladder neck, and in males, the prostatic urethra.

	Required if 1 st urine cytology is suspicious for urothelial carcinoma

## **14.1 Criteria for Response (in Subjects with CIS)**

The primary endpoint for this study is the complete response rate in subjects enrolled in Cohort 1 (see [Section 10](#)). These subjects with CIS will be considered to have a complete response if at the time of any disease status evaluation (per protocol every 13 weeks or any unscheduled evaluation) there is no evidence of high-grade disease (CIS, high-grade Ta or high-grade T1 disease) or disease progression (e.g., to muscle invasive disease). Subjects whose initial diagnosis was CIS who are found to have low-grade papillary disease at the time of an evaluation must have the low-grade disease resected by TURBT. Low-grade disease is not considered a treatment failure in these subjects and they may remain on study treatment following TURBT.

## **14.2 Criteria for Treatment Failure**

As defined in this protocol, the term “treatment failure” will refer to events that demonstrate the study drug Vicinium is not able to achieve or maintain a response in the subject’s bladder cancer. Specifically, the term “treatment failure” in this protocol is being used to define the following events:

1. Diagnosis at study entry was CIS (with or without papillary disease), high-grade Ta disease or high-grade T1 disease:

Subjects whose diagnosis at study entry was CIS or high-grade papillary disease will be considered to have a treatment failure if at the time of any disease status evaluation (per protocol every 13 weeks or any unscheduled evaluation) there is evidence of high-grade disease (CIS, high-grade Ta or high-grade T1 disease) or disease progression (e.g., to muscle invasive disease). Subjects who are found to have low-grade papillary disease at the time of evaluation must have the low-grade disease resected by TURBT. Low-grade disease is not considered a treatment failure in these subjects and they may remain on study treatment following TURBT.

2. Initial diagnosis was low-grade T1 disease:

Subjects whose initial diagnosis was low-grade T1 disease are considered to have a treatment failure if at the time of any disease status evaluation (per protocol every 13 weeks or any unscheduled evaluation) there is evidence of low-grade T1 disease, high-grade disease (CIS, high-grade Ta or high-grade T1 disease) or disease progression (e.g., to muscle invasive disease). Subjects whose initial diagnosis was low-grade T1 disease and who are found to have low-grade Ta disease at the time of evaluation must have the low-grade Ta disease resected by TURBT. Low-grade Ta disease is not considered a treatment failure in these subjects and they may remain on study treatment following TURBT.

3. Subjects with positive urine cytology without histologic, cytologic or radiographic evidence or upper or lower urinary tract malignancy will be considered as no longer in complete response and hence, as having a treatment failure.

### **14.3 Protocol-Defined Events in the Analysis of Event-Free Survival**

Event-free survival (EFS) will be determined for all treated subjects (See [Section 17](#)). Events in the analysis of EFS include:

- Treatment failure as defined in [Section 14.2](#)
- Death (as a first event)

Subjects without evidence of a treatment failure who are diagnosed with upper or lower urinary tract urothelial carcinoma by histology, cytology or radiographic evidence as their first event will be censored in the analysis of EFS at the date of diagnosis.

Subjects without evidence of a treatment failure who undergo cystectomy will be censored in the analysis of EFS at the date of cystectomy.

### **14.4 Criteria for Continuing or Discontinuing Treatment**

The results of cystoscopy and biopsies (as indicated), and urine cytology are used to determine disease status and hence, whether subject may remain on treatment (as long as they are tolerating treatment).

The result of these tests will be classified as follows:

Cystoscopy (based on the investigators assessment)

- Negative (No evidence of disease (NED))
- Suspicious (Apparent or suspicious for disease)

Urine Cytology (based on central cytology reading):

- Negative (Negative for high grade urothelial cancer)
- Atypical urothelial cells (This is not considered suspicious for urothelial cancer)
- Suspicious for high-grade disease

- Unsatisfactory
- Low grade neoplasm

Biopsy Findings (based on central pathology reading):

- Positive (for treatment failure, see [Section 14.2](#))
- Negative (for treatment failure, see [Section 14.2](#)).

## 15 ASSESSMENT OF SAFETY

During the Induction Phase and Maintenance Phase, subjects will be assessed for safety by monitoring of adverse events (AEs), including serious adverse events (SAEs), evaluation of clinical laboratory tests, physical examinations, triplicate ECGs, and vital signs.

### 15.1 Safety Review Plan

Adverse events including serious adverse events, occurring from the time the subject signs the ICF through 30 days after the last dose of study treatment will be recorded on the appropriate electronic CRF(eCRF). This requirement includes AEs from unscheduled as well as scheduled visits.

Adverse events will be monitored by the study Medical Monitor on an ongoing basis. On a quarterly basis (every 3 months), safety tables and listings will be generated for review.

In addition, an independent data safety and monitoring board (DSMB) will be chartered and operate until all subjects have discontinued treatment. The DSMB charter will conform to applicable regulations and guidance. The DSMB will review aggregated safety data. The DSMB chair will also receive all SAE reports upon generation, regardless of attribution. Details of the DSMB structure and function are included in the DSMB charter.

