bladder have been biopsied: the dome, the posterior wall, the left and right lateral walls, the trigone and the bladder neck, and in males, the prostatic urethra. Blood will be drawn at Baseline, during week 12 and after approximately 6 months of therapy for determination of plasma anti-Vicinium antibodies. Blood will be drawn on Day 1 pre-dose and at the end of the 2-hour dwell time, and at the end of the 2-hour dwell time in Week 6 (12th treatment) and Week 12 for the determination of Vicinium plasma levels. Periodic clinical lab tests and pregnancy tests (in females) will be performed.

Additional study procedures will include triplicate ECGs for QTc analysis at completion of the Induction Phase and EpCAM determination by immunohistochemistry on all positive biopsies.

**Post-Treatment Evaluation:** Subjects will return for Post-Treatment evaluations between 30 and 37 days after their last dose of study treatment. Post-treatment procedures include cystoscopy, directed biopsy and urine cytology (if the subject has not discontinued protocol therapy due to disease recurrence or progression and if these evaluations have not been performed in the prior 8 weeks), as well as safety assessments of vital signs, triplicate ECG, physical examination, clinical laboratory analyses, and adverse events and concomitant medications assessments. If a cystoscopy is required, it should be performed as soon as possible on or after Day 30 post-treatment.

**Number of subjects (planned):** Approximately 134 subjects.  $\geq 77$  subjects will enroll in Cohort 1. Up to 57 subjects will enroll in Cohort 2 and Cohort 3 combined.

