### **10.6 Post-Treatment Evaluation**

Subjects will return to the clinic site for a Post-Treatment evaluation 30 – 37 days after their last dose of study treatment.

The following assessments will be performed at that time

- Targeted physical examination (including weight) ([Section 16.3](#))

- Triplicate ECG obtained within 30 minutes of each other at least 3 minutes apart
- Vital signs
- Concomitant medications
- Adverse events, including SAEs
- Collection of clinical laboratory samples: blood samples for hematology and chemistry, urine samples for urinalysis
- Anti-Vicinium antibodies
- Blood or urine pregnancy test (WOCBP)
- The following are to be done if the subject has not discontinued treatment due to documented disease recurrence, progression and if they have not been performed within the past 8 weeks
  - Cystoscopy
  - Biopsy (directed). EpCAM determination by immunohistochemistry will be obtained on all positive biopsies.
  - Urine cytology

As described in **Section 15**, additional follow-up will occur for subjects with ongoing clinically significant AEs (e.g., those leading to study drug discontinuation) or SAEs assessed as related to study drug.

Subjects without a treatment failure (see **Section 14.2**) will continue to undergo evaluations for disease status (urine cytology, cystoscopy, directed biopsies) every 13 weeks until the sooner of a treatment failure or the determination of the 18-month event free survival analysis. Survival data also will be collected on subjects every 13 weeks. Once all subjects are no longer receiving study treatment and the 18-month event-free survival for the study is determined, the study will close and subjects will then be followed by their physician according to standard of care.

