### 15.2 Adverse Events

An adverse event (AE) is defined as any untoward medical occurrence in a subject administered a pharmaceutical product and which does not necessarily have to have a causal relationship with this treatment. An AE can, therefore, be any unfavorable and unintended sign (that may include an abnormal laboratory finding), symptom, or disease temporally associated with the use of a medicinal product, whether or not related to the medicinal product. Any worsening of the subject's pre-existing medical conditions will also be considered an AE, unless it is within the normal range of disease fluctuation for that subject. Pre-existing medical conditions that are stable or improve during the study will be recorded as an AE but will not be considered as treatment-emergent adverse events (TEAEs).

The investigator is responsible for reviewing all laboratory results obtained after a subject signs the ICF through 30 days after the last dose of study drug, whether required by this protocol or for other reasons e.g., evaluation of a pre-existing condition, evaluation and management of an AE. Any abnormal value that leads to a change in the subject's management (e.g., dose interruption, dose reduction, the addition of medication, other medical intervention (e.g., blood transfusion), or increased monitoring) or considered by the investigator to be of clinical significance should be recorded as an AE/SAE.

"Progressive disease" should not be recorded as an AE or SAE. Instead, the diagnoses/syndromes, signs, and/or symptoms associated with a subject's disease progressive should be recorded as AEs, or SAEs if they meet the SAE definition.

All AEs will be assessed using the NCI-CTCAE (version 4.03)  
([http://evs.nci.nih.gov/ftp1/CTCAE/CTCAE\\_4.03\\_2010-06-14\\_QuickReference\\_8.5x11.pdf](http://evs.nci.nih.gov/ftp1/CTCAE/CTCAE_4.03_2010-06-14_QuickReference_8.5x11.pdf)).

AEs for which no appropriate CTCAE term exists will be recorded verbatim from the investigator and graded for severity based on CTCAE definitions:

- Grade 1: Mild; asymptomatic or mild symptoms; clinical or diagnostic observations only; intervention not indicated.
- Grade 2: Moderate; minimal, local or noninvasive intervention indicated; limiting age-appropriate instrumental activities of daily living (ADLs)\*.

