### **15.3 Serious Adverse Events**

A serious adverse event (SAE) or serious suspected adverse reaction is considered serious if, in the view of either the Investigator or sponsor, it results in any of the following outcomes:

- Death;
- A life-threatening AE, defined as an AE that, in the view of either the Investigator or the Sponsor, places the patient or subject at immediate risk of death. It does not include an AE or suspected adverse reaction that, had it occurred in a more severe form, might have caused death;

- A persistent or significant disability/incapacity or substantial disruption of the ability to conduct normal life functions;
- A congenital anomaly/birth defect;
- Inpatient hospitalization or prolongation of existing hospitalization. The following will not be considered as a hospitalization for the criteria of an SAE:
  - Elective or pre-planned hospital stays for conditions that existed prior to informed consent and have not worsened after the subject signed the ICF. However, if any surgical or procedural complication results in prolongation of a pre-planned hospitalization, this must be reported as an SAE.
  - Hospital stays or prolongation of a hospital stay for social reasons.
  - Events that result in a hospital stay or emergency room visit for less than 24 hours if this is the only SAE criterion being met.
  - Routine treatment or monitoring of the studied indication, not associated with any deterioration in condition.
- Important medical events that may not result in death, be life-threatening, or require hospitalization may be considered serious when, based on appropriate medical judgment, they may jeopardize the patient or subject and may require medical or surgical intervention to prevent one of the outcomes listed above. Examples of such medical events include allergic bronchospasm requiring intensive treatment in an emergency room or at home, blood dyscrasias or convulsions that do not result in inpatient hospitalization, or the development of drug dependency or drug abuse.

All SAEs, regardless of suspected causality, occurring from the time a subject signs the Informed Consent and until 30 days after study drug discontinuation must be reported to the sponsor within 24 hours of learning of its occurrence.

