## **15.5 Follow Up of Adverse Events**

Any clinically significant AE (e.g. an AE leading to study drug discontinuation) or any SAE assessed as related to study drug that is ongoing at the time of the Post-Treatment assessment (i.e., 30-37 days after the last dose of study drug) must be followed until either resolution of the event or determination by the investigator that the event has become stable or irreversible. This follow-up guidance also applies to related SAEs that occur >30 days after the last dose of study drug.

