3.3.7. Definitions and Terminology

Adverse Event

An adverse event (AE) is defined as any unfavorable and unintended sign (including an abnormal laboratory finding), symptom or disease temporally associated with the use of a medical treatment or procedure regardless of whether it is considered related to the medical treatment or procedure (attribution of unrelated, unlikely, possible, probable, or definite).

Any medical condition that is present at the time the subject is screened, but does not deteriorate, should not be reported as an AE. However, if it deteriorates at any time during the study it should be recorded as an AE. Hospitalization for elective treatment of a preexisting condition that did not worsen from baseline is not considered an AE or serious AE (SAE).

The descriptions and grading scales found in the revised National Cancer Institute Common Terminology Criteria for Adverse Events (NCI-CTCAE) version 4.03 will be utilized for AE reporting.

Serious Adverse Event

A serious adverse event is any AE that is fatal, life-threatening, requires or prolongs hospital stay, results in persistent or significant disability or incapacity, results in a congenital anomaly or birth defect, or is an otherwise important medical event.

Treatment-emergent AE

Treatment-emergent AEs (TEAEs) are all AEs occurring on or after the date of first dose of study drug through 30 days post the last dose of study drug.

Baseline Value

For purposes of analysis, the baseline value is defined as the last value obtained prior to the first dose of Vicinium.

Study Drug

For the purposes of this study, the term study drug refers to Vicinium.

Day 1 (Baseline)

Day 1 is the day that the first dose of Vicinium is received.

Age

The age of a subject is defined as (Date of Informed Consent – Date of Birth + 1)/365.25.

Study Day

Study Day is defined relative to Baseline (Day 1). Thus, the study day of an event is calculated as:

$$\text{Study Day} = \text{event date} - \text{date of Day 1} + 1.$$

Change from Baseline

Change from baseline for a given endpoint is defined as the Study Day X value minus the Baseline Value.

Cohort 1 Subjects

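### AE recording and the TEAE window close at Day 30, but the final safety visit runs to Day 37, and late related SAEs must be followed without any stated duty to report them to the sponsor

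*Protocol*

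**What the plan says.** Four rules set the end of safety collection:

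- Protocol 15.1 records AEs and SAEs "occurring from the time the subject signs the ICF through 30 days after the last dose of study treatment".
- Protocol 15.2 makes the investigator responsible for "reviewing all laboratory results obtained after a subject signs the ICF through 30 days after the last dose of study drug", and goes on to say which abnormal values become AEs.
- Protocol 15.3 covers SAEs of any causality "until 30 days after study drug discontinuation must be reported to the sponsor within 24 hours of learning of its occurrence". The starting point here is discontinuation, not the last dose.
- SAP 3.3.7 defines TEAEs as those "occurring on or after the date of first dose of study drug through 30 days post the last dose of study drug".

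Two other rules look beyond that point. Protocol 10.6 schedules the "Post-Treatment evaluation 30 – 37 days after their last dose of study treatment"; the Synopsis gives the same interval. The visit includes AE and SAE assessment, hematology, chemistry, urinalysis, triplicate ECG, vital signs and a targeted examination. Protocol 15.5, on following ongoing events to resolution or stability, adds: "This follow-up guidance also applies to related SAEs that occur >30 days after the last dose of study drug".

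**The concern.** The visit meant to close out safety can, on most of its permitted days, take place after the recording window has shut. It matters more than an ordinary end-of-study visit. Chemistry is drawn before doses in late induction and in maintenance, so the Post-Treatment sample will usually be the first scheduled chemistry after the final dose. Table 4 has no ECG during maintenance, so the Post-Treatment ECG is the only scheduled one after Week 12. Any cystoscopy required at this visit is to be done on or after Day 30, so complications of it would mostly begin once the window has closed.

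The second strand is routing. Section 15.5 presupposes that related SAEs after Day 30 become known, and sites will have the chance to learn of them because disease evaluation and survival contact continue every 13 weeks. The sponsor's expedited evaluation (15.4) begins when a report arrives, and the DSMB chair receives SAE reports as they are generated (15.1). If no rule requires the report, both depend on a site volunteering it.

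**Working it through.** No power, alpha or sample-size figure is involved. The check is a day count and a comparison of the rules, with the last dose as Day 0.

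**Day count**

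- Permitted visit days (10.6): 37 − 30 + 1 = 8.
- Permitted days after Day 30: 37 − 31 + 1 = 7.
- Overlap with the windows in 15.1, 15.2 and the SAP TEAE definition: 8 − 7 = 1 day (Day 30 itself).
- Share of permitted days outside: 7/8 = 87.5%.

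**Tracing three kinds of event through the rules**

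1. *Onset by Day 30, found at a Day 31–37 visit.* Section 15.1 turns on when the event occurs, so it must be recorded. It also meets the TEAE definition. Nothing is lost.
2. *New onset on Day 33, for example a raised creatinine first seen that day and dated to the sample.* Section 10.6 requires the sample and the AE enquiry. Section 16.2 has the investigator review all laboratory results, with no day limit. The 15.1 recording rule and the 15.2 review duty have already ended. In the SAP the value can count as a treatment-emergent laboratory toxicity, because that definition takes any post-baseline assessment, but it cannot be a TEAE. If the site records the AE anyway, it appears in the AE listing but not in the AE summary tables of SAP Section 12, which are built on TEAEs.
3. *Related SAE with onset after Day 30.* Section 15.5 requires follow-up. Section 15.1 does not require recording. Section 15.3 does not require a sponsor report, unless discontinuation is dated later than the last dose.

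**The anchor in 15.3**

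If discontinuation is dated *g* days after the last dose, the 15.3 window closes on Day 30 + *g*. It reaches the last permitted visit day only if 30 + *g* ≥ 37, that is *g* ≥ 7. The protocol does not say whether discontinuation means the last dose or the decision to stop, so SAE reporting may or may not outlast AE recording.

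**After aligning the windows**

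If the windows run to the Post-Treatment visit, 0 of 8 permitted days fall outside, against 7 of 8 now. Related SAEs with onset after Day 37 are still not covered, so they need a rule of their own.

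**The case against.** The strongest reply is that onset and detection are different things. A visit on or after Day 30 is well placed to look back over the whole 30-day window, and events that began within it are recordable on any visit day. This stands. A reader might infer that end-of-treatment events in general go unrecorded, or that about 88% of post-treatment assessments cannot yield a recordable AE. The documents support neither. The 87.5% is a share of calendar days, not of events or visits, and nothing says that visits spread evenly. The Synopsis asks for any required cystoscopy as soon as possible from Day 30, which points to early visits.

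Other parts also stand:

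- Day 31–37 values are not lost to analysis. SAP 3.3.8 assigns post-treatment visits to analysis windows, 5.3.3 tabulates laboratory toxicities and shifts, and 5.3.4 summarises QTcF by visit.
- It might be inferred that patients who fail at Week 13 have no safety assessment after induction other than this visit. Table 3 also marks AE assessment at the post-induction evaluation.
- It might be inferred that late related SAEs would never reach anyone. Section 15.3 also has the investigator notify the IRB of all SAEs without a day limit, and 15.4 has the sponsor evaluate every report it receives.
- Running the TEAE window to the visit makes its length depend on scheduling, which a fixed 30 days avoids.

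The reply does not remove the two gaps. Review under 16.2 is not a duty to record an AE. The statement in 15.1 that scheduled and unscheduled visits both count still applies only to events occurring within the window. IRB notification does not send an SAE to the sponsor or the DSMB chair. The SAP cannot cure the gap by analysis, because its own TEAE definition has the same cut-off and it takes precedence over the protocol where they differ.

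**Conclusion.** The plan has a real but limited inconsistency. (a) New events or clinically significant findings with onset on Days 31–37 fall outside the 15.1 recording rule and cannot be TEAEs, although the visit is required to look for them. (b) Related SAEs with onset after Day 30 must be followed under 15.5, but no rule clearly requires them to be recorded or reported to the sponsor, so the 15.4 evaluation and the DSMB chair's review rest on a report that is not required. In addition, 15.2 and 16.2 disagree on how long laboratory results are reviewed, and 15.3 uses a different anchor from 15.1, 15.2 and the SAP.

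The firm figure is 7 of 8 permitted visit days after the cut-off. The number of events affected cannot be estimated, because the documents give no event rates or visit-day distribution. Part (a) assumes that a finding first seen after Day 30 is dated to that day unless the investigator has grounds for an earlier onset. Part (b) is strictest if discontinuation means the last dose. Efficacy conclusions are untouched. The change is worth making because it concerns safety reporting and costs little.

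**What to change.** 1. In 15.3, with a matching sentence in 15.1, require SAEs assessed as related to be recorded and reported to the sponsor within 24 hours of the investigator learning of them, whenever they occur. This lets 15.5, 15.4 and the DSMB arrangement work together.
2. End the windows in 15.1, 15.2 and 15.3 at the later of Day 30 or the Post-Treatment evaluation, all counted from the last dose.
3. Reconcile 15.2 with 16.2, so that the same laboratory results are both reviewed and assessed for AE recording.
4. Use the same end point in the SAP TEAE definition. Alternatively, keep the fixed 30-day TEAE window and tabulate AEs from Day 31 to the Post-Treatment visit separately. This second option keeps TEAE exposure time uniform.

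The cost is wording in both documents and possibly one extra table. No visit is added. For visits held on schedule, the collection window would vary by up to 7 days between subjects, and AE counts may rise slightly.
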